**LIST OF ABBREVIATIONS**

[figure not shown]
ADT	Androgen Deprivation Therapy
AE	Adverse Event
ASCO	American Society of Clinical Oncology
AST	Aspartate Aminotransferase
BM	Bone Marrow

CBC	Complete Blood Count
CMP	Comprehensive Metabolic Panel
CR	Complete Response
CT CA/P	Computed Tomography Scan of Chest Abdomen, and Pelvis
CTCAE	Common Terminology Criteria for Adverse Events
DLT	Dose Limiting Toxicity
DSMB	Data and Safety Monitoring Board
DTCs	Disseminated Tumor Cells
EC	Ethics Committee
ECG	Electrocardiogram
ECOG	Eastern Cooperative Oncology Group
FDA	Food and Drug Administration
GCP	Good Clinical Practice
HIPAA	Health Insurance Portability and Accountability Act
IB	Investigator Brochure
IND	Investigational New Drug
IRB	Institutional Review Board
LDH	Lactate Dehydrogenase
mCRPC	Metastatic Castration Resistant Prostate Cancer
MRI	Magnetic Resonance Imaging
NIST	National Institute of Standard and Technology
PFS	Progression Free Survival
PHI	Protected Health Information
PI	Principle Investigator
PR	Partial Response
PSA	Prostate Specific Antigen
PSADT	Prostate Specific Antigen Doubling Time
PCWG2	Prostate Cancer Working Group 2
RECIST	Response Evaluation Criteria in Solid Tumors
rPFS	Radiographic Progression Free Survival
RSI	Reported Safety Information
SAE	Serious Adverse Event
SD	Stable Disease
SRM	Standard Reference Material
TPP	Time to Tumor Progression

#### STUDY SUMMARY

Title	A pilot study of the combination of 5-azacitidine (5-AZA) and all-trans retinoic acid (ATRA) for prostate cancer with PSA-only recurrence
Short Title	Prostate Cancer Dormancy
Protocol Number	
Phase	Pilot, phase 2
Methodology	Randomized, open label
Study Center(s)	Single-center
Objectives	
Primary
 

1) Evaluate disease progression-free rate at the end of Treatment Phase 1 between 5-AZA+ATRA and no-therapy.

2) Assess safety of the 5-AZA and ATRA combination therapy

 
Secondary:
 

1) Evaluate time to disease progression from start of Treatment Phase 1

2) Correlate antitumor activity and disease progression with biomarkers of dormancy in BM aspirates and peripheral blood

Number of Subjects	20 evaluable patients; the target accrual number is set at 30 to account for screen failures.

Diagnosis and Eligibility Criteria	
Diagnosis: Histologically confirmed adenocarcinoma of the prostate
 
Main inclusion criteria: 1) Rising PSA 2) PSADT <math>\leq</math> 10 months prior to initiation of ADT 2) 3) Received definitive local treatment 4) Indication for ADT 5) No evidence of regional or active distant metastases, except for regional metastases where salvage radiation therapy is not an option
 
Main exclusion criteria: 1) Patients who have received ADT and/or other chemotherapy within 3 months prior to entering the study. 2) Patients who have had radiotherapy or surgery within 4 weeks prior to entering the study. Minimally-invasive procedures for the purpose of diagnosis or staging of the disease are permitted.

Study Product(s), Dose, Route, Regimen	5-azacitidine: 40 mg/m  SQ on days 1-5 All-trans retinoic acid: 45 mg/m  PO daily (divided into 2 doses) on days 3-7 One cycle of treatment: 28 days
Duration of administration	Drugs will be administered on a 28-day cycle
Reference therapy	No reference therapy
Statistical Methodology	We will compare the disease progression-free rate at end of treatment phase 1 and time to disease progression from start of Treatment Phase 1 between 5-AZA+ATRA and no-therapy. Descriptive summary will be provided for safety endpoints and dormancy marker panel. The effect of biomarker abundance on recurrence free survival will be determined using Kaplan-Meier curves stratified across biomarker abundance groups.
Estimated enrollment period	12
Estimated study duration	24 months

## 1. BACKGROUND AND RATIONALE

### 1.1 Disease Background

Prostate cancer (PCa) causes significant morbidity and mortality in the US, disproportionately affecting African American men. The initial treatment for PCa consists of surgical resection and radiation therapy (RT). While these approaches reduce the primary tumor burden, the majority of patients have clinical recurrence and eventually die of metastases several years later. One explanation is the presence of disseminated tumor cells (DTCs) that are resistant to chemotherapy and ADT, but maintain the capacity to reconstitute incurable metastatic disease later in life. In prior studies, DTCs have been shown to survive in BM of PCa patients in a dormant or quiescent (G0/G1 arrest) state and evade therapies. DTCs can be detected in the BM before overt disease is detected, suggesting that DTCs may help us understand how dormancy and reactivation to metastasis occurs. The mechanisms responsible for the onset of dormancy and the transition from DTC dormancy to reactivation have been mostly unknown. Thus, a window of opportunity to target quiescent residual DTCs for elimination or maintenance of dormancy is missed. Our team has pioneered the study of cancer dormancy to understand the biology of DTCs. Based on prior literature and our pre-clinical models, we have developed a treatment strategy with available FDA-approved drugs (5-azacitidine and all-trans retinoic acid) to reprogram DTCs into a dormant state and ultimately, prolong time to clinical disease progression.

### 1.2 Rationale

Our long-term goal is to target the biology of dormant PCa DTCs to prevent relapse of clinical disease. In pre-clinical models, specific micro-environmental cues have been shown to activate a transcription factor (TF) network, which drives epigenetic programs of quiescence and survival in dormant tumor cells. Specifically, ATRA could induce a high p38/ERK activity ratio and dormancy in previously proliferative DTCs through TGF $\beta$ 2 signaling in the BM and through upregulation of BMP7. The p38 activation also induces TFs DEC2 and NR2F1 to induce a dormant state. Overall, the dormancy TF network serves as a signature to predict longer metastasis-free periods and to identify dormant DTCs recovered from BM of prostate cancer patients. Interestingly, many dormancy genes are epigenetically silenced and can be re-expressed using a short-term pulse of low dose 5-AZA, a DNA methylating agent and DNMT1 inhibitor. When we introduced 5-AZA and ATRA in malignant prostate cancer cell lines for three days, many cells displayed upregulation of dormancy biomarkers and the response was maintained for at least 2 weeks.

Our pre-clinical work led us to design a “reprogramming therapy” combining two available FDA-approved drugs (5-AZA, ATRA) to reprogram proliferative cells into stable induced dormant cancer cells (iDCCs). Prior studies with the drugs of interest were performed in castration-sensitive PCa patients with prior exposure to ADT and with fast PSA doubling time (PSADT). We will test if 5-AZA+ATRA extends the progression-free period and delays biochemical and clinical recurrence via induction of PCa cell dormancy. This study will allow us to temporally understand the impact of the reprogramming therapy on the delay in chemical and clinical progression, and to correlate clinical activity with biomarkers of dormancy in DTCs.

Currently, patients who have received definitive local treatment with either RT or surgery undergo serial measurements of PSA to detect early disease recurrence. Such monitoring leads to the identification of men with PSA-only (biochemical) recurrence without evidence of clinical symptoms, or radiographic evidence of recurrent or disseminated disease. Androgen deprivation therapy (ADT) is the standard of care for the initial systemic therapy, however the optimal timing for initiation of ADT remains controversial due to paucity of clinical trial data in this population. Furthermore, ADT causes side effects such as hot flashes, loss of libido, decreased muscle mass, fatigue, and osteoporosis, which can significantly lower the quality of life in otherwise asymptomatic men.

Leuprolide is considered standard of care for prostate cancer with PSA-only recurrence. One dose of Leuprolide has a transient effect of decreasing PSA to negligible levels resulting in a similar baseline for

## Mount Sinai The Tisch Cancer Institute

both groups. Based on historical data, in measuring primary endpoint at 12 weeks, we do not expect Leuprolidet impact disease progression.

To this end, we will conduct a randomized, pilot study in recurrent PCa patients with biochemical recurrence, as defined by rising PSA, of the combination of 5-azacitidine and all-trans retinoic acid to delay disease progression.

### 1.3 Correlative Studies

There is prior literature that shows that DTCs in head and neck squamous cell carcinoma and PCa models could persist in a dormant state in the BM. Mechanistically, we found that TGF $\beta$ 2 mRNA was enriched in naïve BM and in PCa DTCs from patients with no evidence of disease for up to 18 years vs. DTCs from advanced metastatic patients. Upregulation of TGF $\beta$ 2 signaling leads to activation of p38 and its associated quiescence program involving DEC2 and NR2F1. Furthermore, we showed that NR2F1 induces RAR $\beta$  and patients with high levels of NR2F1 and RAR $\beta$  showed longer disease free periods than those with low levels of these transcription factors. We also found that inducible knock down of NR2F1 reactivated DTCs in different organs.

DNA promoter methylation and/or changes in histone-H3 post-translational modifications (PTMs) contribute to NR2F1 silencing proliferative tumor cells and thus, drugs can be used to remodel the epigenome and restore dormancy. ATRA was sufficient to induce NR2F1 and RAR $\beta$  but only transiently, suggesting that other epigenetic changes might be needed to sustain dormancy. Whole genome changes in histone-H3 PTMs occur after low-dose 5-AZA and can be used to rewrite the epigenome for growth suppression. Many aggressive cancer cells including prostate cells treated with 5-AZA+ATRA displayed upregulation of dormancy biomarkers including NR2F1 and RAR $\beta$  mRNAs. We hypothesize that the reprogramming of residual prostate cancer with 5-AZA and ATRA will be a new strategy to prevent or significantly delay time to clinical recurrence compared to current therapies.

## 2. STUDY OBJECTIVES

To our knowledge, no study has evaluated the combination of 5-AZA and ATRA in recurrent PCa. Our hypothesis is that this combination can reprogram DTCs to activate the dormancy pathway and thus delay disease progression, and can be safely tolerated.

### 2.1 Primary Objectives

The co-primary objectives of the study are:

- To compare disease progression-free rate at end of Treatment Phase 1 between 5-AZA + ATRA and no-therapy.
- To assess safety of the 5-AZA and ATRA combination therapy

### 2.2 Secondary Objectives

The secondary objectives are:

- To compare time to disease progression from start of Treatment Phase 1 during the 24-month study period between 5-AZA+ATRA and no-therapy.
- To correlate antitumor activity and progression with biomarkers of dormancy in BM aspirates and peripheral blood.

## 3. STUDY DESIGN

### **3.1 General Design**

This is a prospective, open-label, randomized, pilot study of reprogramming therapy in patients with recurrent PCa based on rising PSA only. Reprogramming therapy will include 5-azacitidine and all-trans retinoic acid. Expected duration of subject participation is 24 months.

All study will be assigned in a 1:1 randomization using computer random number generator to either the '5-AZA+ATRA' group or the 'no therapy' group. All enrollees will receive Leuprolide 7.5 mg x 1 on Day 1. On Day 29, they will initiate treatment phase 1. During this phase, patients in the '5-AZA + ATRA' group will receive treatment on a 28-day cycle, in the absence of prohibitive toxicities, for 3 cycles. During treatment phase 2, the 'no therapy' group will receive 5-AZA + ATRA on a 28-day cycle, in the absence of prohibitive toxicities, for 3 cycles. The treatment effect will be determined via comparing the intra-individual disease progression outcome at the end of the treatment phase 1, with period effect being separated through randomization. After treatment phase 1 and phase 2, all patients will be followed for a total of 24 months from the start of the study or until the events leading to discontinuation as outlined in Section 7.1 are observed. 5-AZA will be given subcutaneously on days 1-5 at a dose of 40 mg/m^2. ATRA, dosed at 45 mg/m^2 daily (divided into 2 doses), will be taken orally on days 3-7 of each cycle.

### **3.2 Primary study endpoints**

The primary clinical endpoints of this study are the disease progression-free rate at the end of treatment phase 1 and safety of the combination of 5-AZA and ATRA. Disease progression is defined as a composite of PSA or radiographic progression.

#### **3.2.1 PSA Progression**

PSA Progression is as defined by PCWG2 criteria. Baseline PSA will be defined as the serum PSA level measured prior to start of treatment.

In patients who have a decline in PSA value from baseline, progression is defined by:

- An increase in PSA by 25% above the nadir, AND
- An increase in PSA by a minimum of 2 ng/ml, or an increase in PSA to the pre-treatment PSA value, AND
- Confirmation by a second PSA at least 3 weeks apart, AND
- There is no objective evidence of disease response.

In patients whose PSA value has not declined from baseline, progression is defined by:

- An increase in PSA by 25% above either the pre-treatment level, or the nadir PSA level (whichever is lowest), AND
- An increase in PSA by a minimum of 2 ng/ml, AND
- Confirmation by a second PSA at least 3 weeks apart, AND
- There is no objective evidence of disease response.

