## **8. STATISTICAL CONSIDERATIONS**

### **8.1 Study Design/Study Endpoints**

The primary endpoints will be the disease progression-free rate at the end of the treatment phase 1 and safety of the combination of 5-AZA and ATRA. Disease progression is defined by composite of PSA or radiographic progression relative to period baseline (start of treatment phase 1), whichever occurs first. PSA levels will be measured on day 1 of each cycle. For assessment of PSA progression, see section 3.2.1 above. CT A/P and bone scan will be performed every 3 cycles. For assessment of radiographic progression, see section 3.2.2 above. Safety will be assessed by the recording of adverse events, monitoring of vital signs and physical examinations, safety laboratory evaluations, and 12-lead ECG. Adverse events will be graded per the Common Terminology Criteria for Adverse Events (CTCAE) version 4.0. Therapy will be continued at the original dose if the adverse event is grade 0-2. For grade 3-4 toxicities, therapy will be held until improvement of symptoms to grade 2 or below. The dose will then be reduced by 25% of original for each episode. A maximum of 2 dosage reductions will be allowed. The third occurrence will result in removal of the patient from the study.

The secondary endpoints will be time to tumor progression from start of treatment phase 1 and the measurement of dormancy biomarker levels in relation to disease states: tumor progression and disease progression. To determine the relation between dormancy biomarkers and disease states, every 3 cycles, we will measure the dormancy biomarkers, TGF $\beta$ 2, BMP7, BMP4, GAS6, retinoic acid, NR2F1, in BM aspirates and peripheral blood.

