### **8.2 Sample Size and Accrual**

The primary endpoint is disease progression free rate at the end of treatment phase 1. Disease progression is defined as either PSA progression or radiographic progression relative to baseline. The baseline value is defined as the PSA level at the beginning of treatment phase 1 (Day 29 of study). The previous Phase II studies on 5-AZA and ATRA individually demonstrated their efficacy in delaying PSA rise among prostate cancer patients. Preclinical in-vivo study demonstrated that in adjuvant setting following primary tumor surgery, animals treated with the drug combination for 4 weeks have 73% reduction on the median cell count of disseminated tumor cells in lung comparing to control animals (Personal communications between [name] and [name]).

Thus, we assume the difference in progression free rates at end of the treatment periods between drug combination and no-therapy ranges between 30% to 60% and listed various scenarios of progression-free rates in Table 1. We use McNemar test statistic to calculate the range of sample size required to differentiate the treatment from no-therapy under each scenario. The maximum sample size is required when the PSA rise is independent in the two treatment periods for the same patient. The minimum sample size is required when the PSA progression status in the two treatment periods is highly concordant. With the planned 20 patients in total, we would have >80% power to detect the difference of PSA progression rate of 20% vs 60%, with two-sided type I error of 10%. All calculation was done using PASS software.

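### On the leuprolide-suppressed Day 29 baseline, the two PSA-progression branches misorder patients, and the 20-30% progression-free rate behind the sample size has no stated PSA basis

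*Combined protocol and SAP*

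**What the plan says.** **Baseline.** Section 8.2: "The baseline value is defined as the PSA level at the beginning of treatment phase 1 (Day 29 of study". Section 8.1 agrees, judging progression "relative to period baseline (start of treatment phase 1". Section 3.2.1 names no day: "Baseline PSA will be defined as the serum PSA level measured prior to start of treatment".

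**PSA level at that baseline.** Everyone receives leuprolide on Day 1 (Section 3.1). Section 1.2 says: "One dose of Leuprolide has a transient effect of decreasing PSA to negligible levels". No ng/ml value and no recovery time is given.

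**Progression rule (Section 3.2.1).**
- After a decline from baseline: "An increase in PSA by 25% above the nadir, AND" then "An increase in PSA by a minimum of 2 ng/ml, or an increase in PSA to the pre-treatment PSA value".
- With no decline: "An increase in PSA by 25% above either the pre-treatment level, or the nadir PSA level (whichever is lowest), AND" then a rise of at least 2 ng/ml, with no alternative.
- Both branches need a confirming PSA at least 3 weeks apart. PSA is drawn every 4 weeks.

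**Sample size.** Section 8.2 says "we assume the difference in progression free rates at end of the treatment periods" is 30 to 60 points. Its Table 1 uses P1 = 0.2 to 0.3 and P2 = 0.6 to 0.8. It does not say which is control, and the text then describes 20% vs 60% as a rate of PSA progression.

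**The concern.** A progression rule should rank a worse PSA course as worse. When PSA starts near zero, returning to the starting value can be a rise of a few hundredths of a ng/ml, while the 2 ng/ml floor is a many-fold rise. A patient who dips and recovers is then an event, and a patient whose PSA climbs steadily is not.

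The primary endpoint is binary and is planned in 20 evaluable patients, so a few such classifications could change the result. The branch a patient enters is also related to treatment. Section 5.1.5 reports PSA declines in 14 of 36 evaluable patients on 5-azacitidine in an earlier phase II trial.

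The same baseline feeds the sample size. If P1 is the control progression-free rate, 70-80% of untreated men must progress within 12 weeks. Whether they do depends on how low PSA is at Day 29 and how fast it recovers.

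**Working it through.** **1. The plan's power figure.** Inputs from Section 8.2: 20% vs 60%, two-sided alpha 0.10, N = 20. McNemar normal approximation:

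n = [z(0.95)·√ψ + z(0.80)·√(ψ − d²)]² / d², with d = 0.4.

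- Independent periods: ψ = 0.2×0.4 + 0.6×0.8 = 0.56, so n = [1.645×0.748 + 0.842×0.632]²/0.16 = 19.4. Power at N = 20 is 81.1%.
- Full concordance: ψ = d = 0.4, so n = 13.2. Power at N = 20 is 93.7%.

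The stated range of 14-19 and power above 80% therefore reproduce. Reading 20% vs 60% as progression rates (progression-free 80% vs 40%) gives the same ψ and d, so this calculation cannot show which label was meant.

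**2. Thresholds implied by Section 3.2.1.** With Day 29 PSA b and nadir n:

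- No decline: max(1.25b, b + 2).
- Decline: max(1.25n, min(n + 2, b)).

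| Day 29 PSA (ng/ml) | No decline: progresses at | Fold rise | Dip to half: progresses at | 10% dip: progresses at |
|---|---|---|---|---|
| 0.1 | 2.1 | 21 | 0.1 | 0.1125 |
| 0.2 | 2.2 | 11 | 0.2 | 0.225 |
| 0.5 | 2.5 | 5 | 0.5 | 0.5625 |
| 1.0 | 3.0 | 3 | 1.0 | 1.125 |

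A return to exactly b counts only if the nadir was at most 80% of b (1/1.25).

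**3. Worked courses** (Day 29, then weeks 4, 8 and 12; no objective response):

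- 0.20, 0.15, 0.20, 0.20: 0.20/0.15 = 1.33, at least 1.25, and back at baseline at week 8, confirmed at week 12. **Progression.**
- 0.20, 0.80, 1.50, 2.10: the threshold is 2.20 and is never reached, although PSA has risen 10.5-fold. **Progression-free.**
- 0.20, 0.18, 0.80, 1.50: the threshold is 0.225, passed at week 8 and confirmed at week 12. **Progression.**
- 0.20, 0.22, 0.80, 1.50: the threshold is 2.20. **Progression-free.**

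The last two differ only by 10% either side of baseline at week 4.

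**4. What the 2 ng/ml floor needs without rebound.** Assume growth at a constant doubling time, and confirmation by week 12. With 4-weekly PSAs the rise must then be present by week 8 (56 days).

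Doubling time in months = 56 / log2((b + 2)/b) / 30.44.

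- b = 0.1: 56/4.39/30.44 = 0.42
- b = 0.5: 56/2.32/30.44 = 0.79
- b = 1.0: 56/1.58/30.44 = 1.16

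Eligibility is a doubling time of at most 10 months and the stratification cut is 3 months. At 3 months the 8-week growth factor is 2^(1.84/3) = 1.53, so Day 29 PSA would have to be at least 2/0.53 ≈ 3.78 ng/ml. These figures cover the PSA component only.

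**5. What rebound does to the control rate.** This simulation is illustrative and every input is assumed: pre-leuprolide median PSA 0.5 to 10 ng/ml (log-SD 0.9), Day 29 PSA at 5% or 30% of that, recovery by week 8, 12 or 24, doubling time 1 to 10 months, 10% assay CV, confirmation by week 12. Control progression-free rates:

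- No further fall after Day 29: 0.84-1.00 at median 0.5; 0.32-0.99 at median 2; 0.01-0.75 at median 10.
- Further 50% fall after Day 29: 0.00 with recovery by week 8-12; 0.18-0.91 with recovery by week 24.

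Some scenarios land on the plan's range. For example, median 10, Day 29 at 5%, no further fall and recovery by week 12 gives 0.20.

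**6. What a wrong rate would cost.** If control were 80% and treated 95% progression-free (hypothetical), the formula in step 1 gives N = 40-62, and 20 patients give about 40% power under independence.

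**The case against.** **The assumed rate could be right.** A reader might infer from step 4 that a 20-30% control rate is impossible. The documents do not support that. Section 1.2 calls the leuprolide effect transient, so rebound is part of the plan's own premise, and step 5 shows that rebound can produce such a rate. Controls whose PSA keeps falling after Day 29 also enter the easier branch, which lowers the control rate further. Radiographic progression adds events too.

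**Bias against the drug is not shown.** A reader might infer it, since a drug that lowers PSA puts patients in the easier branch. But both arms receive leuprolide, so controls may dip as well. A decline is not itself an event, and an effective drug should prevent the return to baseline. The net direction is unknown.

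**Confirmation narrows the route.** If it must fall within the 12 weeks, dip-and-return needs a dip at week 4, a return at week 8 and a confirming value at week 12. That is right, and the courses in step 3 respect it.

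**It is a published criterion.** Section 3.2.1 adopts it by citation. The cited title concerns men with castrate testosterone levels, whereas this trial gives a single leuprolide dose, so adoption does not settle whether the rule suits a Day 29 baseline.

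**Pre-treatment might mean pre-leuprolide.** Section 3.2.1 allows that reading. Most patients would then be in the decline branch and the asymmetry would largely disappear. Sections 8.1 and 8.2 point to Day 29, however. That the choice of reading decides who has progressed is itself a reason to settle it.

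**Conclusion.** The misordering follows from the plan's wording once baseline is Day 29 and PSA is low there; it needs no assumption about rebound. At 0.1 ng/ml the progression threshold is 2.1 ng/ml without a dip, 0.1125 after a 10% dip and 0.1 after a dip to half. The gap narrows as Day 29 PSA rises, so its practical size depends on a value that the plan describes only in words.

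The control rate is unsupported rather than refuted. Reading P1 as control is the natural reading of the sample-size table, but the text of Section 8.2 leaves it open. Under the assumed scenarios the rate runs from 0% to 100%.

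A reader might also infer an error in the power calculation. The figure for 20% vs 60% reproduces by the normal approximation; the weakness is in its input. This should be corrected, as an endpoint definition and an undocumented assumption.

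**What to change.** 1. **One baseline and one criterion.** In Sections 3.2.1, 8.1 and 8.2, name the same baseline for the Phase 1 endpoint. Apply one PSA criterion to every patient: at least 25% and at least 2 ng/ml above the lowest value from Day 29 onward, confirmed, without the alternative of returning to the Day 29 value. State whether confirmation must fall by week 12.
2. **Supportive analysis.** Add the log-PSA slope from Day 29 to the end of Treatment Phase 1, compared by arm, using the 4-weekly PSAs already scheduled.
3. **Sample-size basis.** In Section 8.2, label P1 and P2 by arm and as progression or progression-free. State the Day 29 PSA and the rebound assumed for the control rate, or restate the rate and the sample size that follows.

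**Cost.** Wording in three sections and one extra analysis, with no new visits or samples. The endpoint would depart from the criteria as now written. The single rule removes the misordering between branches, but the 2 ng/ml floor stays insensitive at low PSA: the course 0.20, 0.80, 1.50, 2.10 would still be progression-free. The slope analysis is added for that reason.
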